3.1 Eligibility Criteria

- 3.1.1 Patients must have histologically or cytologically confirmed LCH, ECD or HS. Confirmation of outside pathology at BWH will be performed but is not mandatory prior to study enrollment (see section 3).
- 3.1.2 Detectable disease by at least one of the following modalities: CT, PET, bone scan, or MRI.
- 3.1.3 Patients with LCH must require systemic therapy according to the Histiocyte Society LCH Evaluation and Treatment Guidelines (HS 2009) Or Patients with HS requiring systemic treatment as defined by disease that cannot be surgically resected and/or encompassed in a single radiation field.
- 3.1.4 Age 18 years or older.
- 3.1.5 ECOG performance status ≤ 2 (Karnofsky $\geq 60\%$, see Appendix A)
- 3.1.6 Participants must have normal organ and marrow function as defined below:

_	absolute neutrophil count	≥1,000/mcL
_	platelets	≥100,000/mcL
-	total bilirubin	within 1.5 times normal institutional limits
-	AST(SGOT)/ALT(SGPT)	$\leq 3 \times$ institutional upper limit of normal
-	creatinine	within 2 times normal institutional limits
		OR
-	creatinine clearance	\geq 30 mL/min/1.73 m ² . Note, dose adjustments are
		required for $CrCl \ge 30$ mL/min but ≤ 60 ml/min.

- 3.1.7 Able to take aspirin 81 mg daily as prophylactic anticoagulation if not on warfarin, low molecular weight heparin or oral factor Xa inhibitor. Patients intolerant to ASA may use warfarin or low molecular weight heparin at doses designed to treat deep venous thrombosis.
- 3.1.8 All study participants must be registered into the mandatory Revlimid REMS® program, and be willing and able to comply with the requirements of the REMS® program.

- 3.1.9 Women of child-bearing potential and men must agree to use adequate contraception (hormonal or barrier method of birth control; abstinence) prior to study entry and for the duration of study participation.
- 3.2.0 Ability to understand and the willingness to sign a written informed consent document.

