5.1 Treatment Regimen

For cycle 1, lenalidomide will be administered at a dose of 10 mg daily on days 1-21 of a 28 day cycle. Patients will be assessed for toxicity between days 22 and 28. If no grade 3 or greater toxicity has occurred the dose will be escalated to 25 mg daily on days 1-21 of a day 28 cycle (patients with a baseline CrCl of 30 to ≤ 60 will stay at the 10 mg dose). Patients with a baseline CrCl of 30 to ≤ 60 can be dose escalated to 25 mg if there is no grade 3 or greater toxicity at week 8 visit if CrCl has improved to >60. No dose escalated unless it is a toxicity due to neutropenia in which case the dose can be escalated if there is no recurrent neutropenia with growth factor support for two continuous cycles. Treatment will be administered on an outpatient basis. The maximum number of cycles is 12 (inclusive of cycle 1 and/or 2 dosing at 10 mg). Reported adverse events and potential risks are described in Section 7. Appropriate dose modifications are described in Section 6. No investigational or commercial agents or therapies other than those described below may be administered with the intent to treat the participant's malignancy.

Agent	Premedications; Precautions	Dose	Route	Schedule	Cycle Length
Lenalidomide	None	10 mg tablet (cycle 1)*	PO at approximately the same time each day(+/- 2 hours)	Days 1-21	28 days
Lenalidomide	None	25 mg tablet (cycle 2 and subsequent)*	PO at approximately the same time each day	Days 1-21	

The participant will be requested to maintain a medication diary of each dose of medication. The medication diary will be returned to clinic staff at the end of each cycle.

5.2 **Pre-Treatment Criteria**

5.2.1 Cycle 1, Day 1

Participants must meet all of the inclusion criteria, have none of the exclusion criteria, and must be registered to the protocol prior to initiating therapy.

The following studies and evaluations should be carefully reviewed to determine the patient's suitability to initiate study treatment.

- 1. Diagnosis of LCH, ECD, or HS is established by disease evaluations and laboratory studies and confirmed histologically
 - 2. Complete physical examination.
 - 3. Medical history: Detailed documentation of disease and treatment history with outcomes.
 - 4. Performance status $\geq 60\%$
 - 5. Concurrent medical conditions.
 - 6. Hematology: CBC with automated differential.

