5.2.2 Subsequent Cycles

A new course of treatment may begin on the scheduled Day 1 of a new cycle if:

- The ANC is \geq 1000/mm³;
- The platelet count is \geq 75,000 /mm³
- Any drug-related rash that may have occurred has resolved to \leq grade 1 severity
- Any other drug-related adverse events that may have occurred have resolved to \leq grade 2 severity.

If these conditions are not met on Day 1 of a new cycle, the subject will be evaluated weekly and a new cycle of treatment will not be initiated until the toxicity has resolved as described above. If a given toxicity has not resolved to an acceptable level within 28 days of the planned initiation of a cycle, the participant will be permanently removed from treatment.

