5.3 Agent Administration

In general, there is a +/- 3 day window for lenalidomide administration to allow for scheduling related issues.

Lenalidomide

Celgene Corporation will supply lenalidomide to study participants at no charge through Celgene's Revlimid Risk Evaluation and Mitigation Strategy[™] (REMS) (formerly known as RevAssist® Program). Lenalidomide will be supplied as capsules for oral administration and will be taken on days 1-21 of a 28 day cycle. The first cycle will be dosed at 10 mg with a dose escalation to 25 mg at cycle 2 in the absence of toxicity. If the creatinine clearance is 30 to \leq 60 then the starting dose will be still be 10 mg at cycle 2. In the absence of grade 3 or greater toxicity during cycle 1 the dose will stay at 10 mg during cycle 2 in this patient population. In the absence of grade 3 or greater toxicity at the week 8 assessment the dose can be escalated to 25 mg daily on days 1-21 of a 28 day cycle in patients whose baseline CrCl was 30 to \leq 60 and in whom CrCl subsequently improves to >60. No dose escalation if permitted after week 8. The maximum number of cycles is 12 inclusive of the dose escalation cycle(s). Lenalidomide will be taken at approximately the same time every day (+/-2 hours) and there are no dietary considerations. Vomited doses will not be made-up. Missed or forgotten doses can be made up if taken within twelve hours of the scheduled administration on the same calendar day. For example, if the patient is scheduled to take lenalidomide at 8 AM a missed dose can be made up prior to 8 PM on the day of treatment. However, if the patient was scheduled to take a dose at 4 PM and that dose is missed, the dose must be taken before midnight of the same calendar day. If

these conditions cannot be fulfilled the dose should be skipped.

Packaging

Lenalidomide will be shipped directly to patients from a specialty pharmacy. Bottles will contain a sufficient number of capsules for one cycle of dosing. Lenalidomide supplies are dispensed in individual bottles of capsules. Each bottle will identify the contents as study medication. In addition, the label will bear Celgene's name, quantity contained and the standard caution statement as follows: "Caution: New drug - Limited by Federal law to investigational use." The study drug label must be clearly visible. Additional labels must not cover the Celgene label.

Return

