5.4 General Concomitant Medication and Supportive Care Guidelines

Anti-emetics will be prescribed per physician and patient preference with the exception that steroids should not be utilized as an anti-emetic. If patients require glucocorticoids for any reason during treatment they should be removed from the protocol unless the expected duration of treatment is less than 7 days and the glucocorticoids will not be given on a recurring basis. Erythroid growth factors are not permitted on protocol due to concerns about augmenting clotting risk. Filgrastim and pegfilgrastim are not permitted during cycle 1 but are permitted during the second and subsequent cycles as outlined in section 6 on dose modification (note, filgrastim and pegfilgrastim are not allowed during the first 8 weeks in patients with a CrCl of 30 to ≤ 60).

Because there is a potential for interaction of lenalidomide with other concomitantly administered drugs through the cytochrome P450 system, the case report form must capture the concurrent use of all other drugs, over-the-counter medications, or alternative therapies.

Lenalidomide is known to increase the risk of arterial and venous thrombosis. Patients not already on systemic anticoagulation (warfarin, low molecular weight heparin, or equivalent) for other medical reasons are required to take aspirin 81 mg daily for the duration of the study.

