Grade 4	 and reduce the dose of lenalidomide by 1 dose level at the start of the next cycle. Omitted doses are not made up. If Grade 4, discontinue lenalidomide. Remove patient from study.
Venous thrombosis/embolism ≥ Grade 3	 Hold (interrupt) lenalidomide and start therapeutic anticoagulation, if appropriate. If VTE occurs while patient is on therapeutic anti-coagulation (not counting aspirin) permanently discontinue treatment. Restart lenalidomide at investigator's discretion (maintain dose level). See Anticoagulation Consideration (Section 5.6.1.2)
Hyperthyroidism or hypothyroidism	 Omit lenalidomide for remainder of cycle, evaluate etiology, and initiate appropriate therapy. See Instructions for Initiation of a New Cycle and reduce the dose of lenalidomide by 1 dose level.
Other non- hematologic toxicity ≥ Grade 3	 Hold (interrupt) lenalidomide dose. Follow at least weekly. If the toxicity resolves to ≤ grade 2 prior to Day 21 of the current cycle, restart lenalidomide and continue through the scheduled Day 21 of the current cycle. Otherwise, omit for remainder of cycle. Omitted doses are not made up. For toxicity attributed to lenalidomide, reduce the lenalidomide dose by 1 dose level when restarting lenalidomide.

Table 4. Tumor Flare Reaction Treatment (TFR)

Treatment of TFR is up to the discretion of the investigator, depending upon the severity and clinical situation. It is suggested that Grades 1 and 2 TFR be treated with NSAIDs (i.e., ibuprofen 400 to 600 mg orally every 4 to 6 hours as needed), corticosteroids, and/or narcotic analgesics for pain management.

In mild to moderate (Grades 1 and 2) cases, it is suggested that study drug be continued along with symptomatic treatment as above. In more severe cases, study drug should be interrupted.

Tumor Flare Reaction (TFR) ^a Grades 1-2	 Continue lenalidomide, maintain dose level At the investigator's discretion may initiate therapy with NSAIDs, limited duration corticosteroids, and/or narcotics
Grades 3-4	 Hold (interrupt dose) and initiate therapy with NSAIDs, corticosteroids, and/or narcotics When symptoms resolve to ≤ Grade 1, restart at same dose level for the rest of the Cycle

Treatment of Overdose

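### The renal dose limit is keyed to baseline CrCl: 5.1 and 5.3 can disagree at cycle 2, and no dose is set if CrCl falls to 30 to ≤ 60 after escalation to 25 mg

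*Combined protocol and SAP*

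**What the plan says.** - **3.1.6** attaches a note to the eligibility limit for creatinine clearance: dose adjustments are "required for $CrCl \ge 30$ mL/min but ≤ 60 ml/min". It names neither a dose nor a time of measurement.
- **5.1** gives 10 mg in cycle 1 and directs escalation to 25 mg if there was no grade 3 or greater toxicity. The renal exception is "patients with a baseline CrCl of 30 to ≤ 60 will stay at the 10 mg dose".
- **5.3** restates the cycle 2 rule. One sentence assigns 10 mg at cycle 2 to a CrCl of 30 to ≤ 60 without saying when CrCl is measured. The paragraph then continues about that same group and allows 25 mg at week 8, absent grade 3 or greater toxicity, for patients in the band at baseline "and in whom CrCl subsequently improves to >60". It closes with "No dose escalation if permitted after week 8" (evidently meaning that none is permitted).
- **5.4** uses the band, also without a time of measurement, but only for growth factors: "filgrastim and pegfilgrastim are not allowed during the first 8 weeks in patients with a CrCl of 30 to ≤ 60".
- **5.2.2** has no renal condition for starting a cycle. Its general item reads "Any other drug-related adverse events that may have occurred have resolved to" grade 2 or lower.
- **Section 6, Table 3** has no renal row. The nearest is "Other non- hematologic toxicity ≥ Grade 3", which holds the drug and adds: "For toxicity attributed to lenalidomide, reduce the lenalidomide dose by 1 dose level when restarting lenalidomide".
- **Section 6** also sets a floor of 10 mg once a patient has been escalated, allows three reductions from 25 mg, and bars re-escalation after a reduction except in a defined neutropenia case.

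**The concern.** The plan treats CrCl of 30 to ≤ 60 as a reason for a lower dose. Section 2.2 reports that about two-thirds of the drug leaves unchanged in urine (healthy volunteers). The plan also accepts that CrCl can change on treatment, because it releases a patient at week 8 if CrCl has risen above 60. It has no matching rule for a fall. Decline is foreseeable: Section 7.1 lists renal failure and dehydration among the frequently reported events, whatever their cause.

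Two patients with the same current CrCl can therefore be on different doses because of where they started. At cycle 2, two investigators could also give the same patient different doses, each relying on a sentence in the protocol.

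**Working it through.** The plan states no figure to reproduce. The check is to run cases through the rules and then do simple dose arithmetic. The CrCl values 65, 55 and 45 are illustrative.

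**Step 1. Cases, assuming no grade 3 or greater toxicity unless stated.**

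| Case | 5.1 | 5.3 | Result |
|---|---|---|---|
| Baseline 55, C2D1 45 | 10 mg | 10 mg | Agree |
| Baseline 65, C2D1 45 | 25 mg | 10 mg if the undated sentence means current CrCl; no separate rule if it means baseline | Ambiguous or in conflict |
| Baseline 65, on 25 mg, later falls to 45 | No rule | No rule | Stays at 25 mg |
| Baseline 55, released at week 8 to 25 mg, later falls to 45 | No rule | No rule | Stays at 25 mg |

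**Step 2. Which reading of 5.3?** The sentences after the undated one refer back to its group and then describe that group by baseline CrCl, so baseline is the more natural reading. If current CrCl was meant, a patient held for a new fall has no way back. The week 8 release names only patients in the band at baseline, and later escalation is barred.

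**Step 3. Do other provisions supply a dose after escalation?**
- 5.2.2 can delay a cycle only for a drug-related event above grade 2.
- The Table 3 general row needs grade 3. If the event is attributed to lenalidomide, the dose drops one level in Table 1, from 25 to 20 mg, which is 20/10 = 2.0 times the dose used for the band. If it is not attributed, the row requires no reduction.
- 5.5 lets the investigator stop therapy but sets no lower dose.
- Section 10 asks for repeat laboratory tests when a patient is deteriorating, which may detect a fall but does not set a dose.

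**Step 4. Size.** The daily ratio is 25/10 = 2.5. Assume full dosing and a fall on day 1 of cycle k. The planned doses from then to cycle 12 are (13 − k) × 21 × 25 mg and (13 − k) × 21 × 10 mg.

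| Fall at | At 25 mg | At 10 mg | Status |
|---|---|---|---|
| C2D1 | 11 × 525 = 5,775 mg | 11 × 210 = 2,310 mg | Only if 5.1 prevails over 5.3 |
| C3D1 | 10 × 525 = 5,250 mg | 10 × 210 = 2,100 mg | Gap not in dispute |
| C12D1 | 525 mg | 210 mg | Gap not in dispute |

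**Step 5. Can current CrCl be used with the existing schedule?** The Section 10 calendar has serum chemistry at C2, C3, C4, C6, C8, C9 and C12 day 1, which is 7 of the 11 cycle starts from C2 to C12. The longest gap between these draws is C9D1 to C12D1, 3 × 28 = 84 days.

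**The case against.** **Cycle 2.** The undated sentence in 5.3, read as literally as 5.1, keeps the patient who fell from 65 to 45 at 10 mg. A reader might infer that no provision at all bears on a fall in CrCl and that the protocol plainly escalates such a patient. The text does not support that. At cycle 2 the most that can be said is that 5.1 and 5.3 are ambiguous or conflict. This objection stands.

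**Eligibility note.** A reader might also infer that escalating such a patient breaches 3.1.6. That note belongs to an entry criterion. It shows that the plan regards the band as needing adjustment, but it does not itself set an on-treatment rule. This stands too.

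**Missing text.** Both rows of the 5.1 dosing table carry an asterisk whose footnote is absent from the text reviewed, and the 5.1 sentence on escalation and neutropenia appears to have lost words. Absence can be claimed only for the text available, so the footnote must be checked first.

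**Scale.** This is a 12-patient pilot with creatinine already scheduled and investigator discretion to stop. That limits the importance of the point, but discretion to stop is not a dose, and none of these objections supplies one for a fall after escalation.

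**Conclusion.** The point holds in two parts. At cycle 2, 5.1 and 5.3 can give 25 or 10 mg to the same patient. After escalation, the available text sets no reduced dose for a fall to 30 to ≤ 60 short of a grade 3 or greater event or a decision to stop.

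The contrast is 2.5 times in daily dose. The cumulative difference depends on timing, from 525 against 210 mg for a fall at C12D1 up to 5,250 against 2,100 mg at C3D1. The larger C2D1 figure applies only if 5.1 governs.

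A reader might infer that exposure or toxicity would also be 2.5 times as high, or that the efficacy conclusion is at risk. The documents give no exposure or toxicity by CrCl and no basis for counting how many of the 12 patients would cross 60 downward. The rule of three responses in 12 is not altered. The conclusion assumes that the missing table footnote does not already address a fall on treatment. Subject to that, it should be corrected.

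**What to change.** Check the footnote to the 5.1 dosing table first. If it does not cover the case:

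1. **5.1 and 5.3, cycle 2.** Base escalation on both baseline CrCl and the latest CrCl before C2D1 dosing, repeating the creatinine if the value has newly fallen into the band. Hold at 10 mg if either is 30 to ≤ 60. Apply the existing week 8 release (CrCl >60, no grade 3 or greater toxicity) to everyone held.
2. **Table 3, new row.** A confirmed fall to 30 to ≤ 60 on a dose above 10 mg means reduce to 10 mg. Later toxicity reductions follow Table 2 (5 mg, then 2.5 mg). This needs a stated exception to the 10 mg floor in Section 6, and a statement on whether the renal step counts toward the three permitted reductions. Also say what to do below 30, for example hold.
3. **Recovery.** State whether the prior dose may resume once CrCl is >60. If so, write it as an exception both to the 5.3 bar on escalation after week 8 and to the Section 6 bar on re-escalation after a reduction. Give patients held at cycle 2 the same route.

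Where no chemistry is scheduled (C5, C7, C10, C11), use the latest value. The growth-factor limit in 5.4 need not change.

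**Cost.** Wording, one table row, the exception sentences, and one repeat creatinine per crossing. Some patients will receive less drug. Against a full plan of 210 + 11 × 525 = 5,985 mg, one extra cycle at 10 mg costs 21 × 15 = 315 mg (5.3%). A reduction from C4D1 with no resumption gives 210 + 2 × 525 + 9 × 210 = 3,150 mg (47.4% less). A patient held at 10 mg throughout gets 12 × 210 = 2,520 mg (57.9% less). The recovery rule therefore matters as much as the reduction.

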5.2.2 Subsequent Cycles

A new course of treatment may begin on the scheduled Day 1 of a new cycle if:

- The ANC is \geq 1000/mm³;
- The platelet count is \geq 75,000 /mm³
- Any drug-related rash that may have occurred has resolved to \leq grade 1 severity
- Any other drug-related adverse events that may have occurred have resolved to \leq grade 2 severity.

If these conditions are not met on Day 1 of a new cycle, the subject will be evaluated weekly and a new cycle of treatment will not be initiated until the toxicity has resolved as described above. If a given toxicity has not resolved to an acceptable level within 28 days of the planned initiation of a cycle, the participant will be permanently removed from treatment.

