1. OBJECTIVES

This is an open-label phase II study to evaluate the efficacy and safety of lenalidomide in participants with relapsed/refractory ECD or LCH and in any patient with HS requiring systemic therapy. Patients will receive up to 12 cycles of lenalidomide with treatment occurring on days 1-21 of each 28 day cycle. In cycle one patients will receive lenalidomide 10 mg daily due to the unknown incidence of tumor flare in this population (tumor flare has been observed in other diseases such as chronic lymphocytic leukemia). Patients who tolerate the 10 mg dose well will be escalated to 25 mg for future cycles. There will also be the possibility of dose reduction for patients who do not tolerate the 10 mg starting dose. Dosage thereafter will be adjusted based upon toxicity. Lenalidomide is known to increase the risk of venous and arterial thromboembolic events. Patients not already receiving systemic anticoagulation for other clinical indications will be required to take aspirin 325 mg daily for the duration of the protocol or for one month following treatment discontinuation, whichever is longer.

Disease assessments will occur at baseline and then again at cycle 3 day 1, cycle 6 day 1, cycle 9 day 1 and cycle 12 day 1 as well as every 3 months thereafter until month 24 from study initiation when disease assessment will occur every 6 months until month 36 from the initiation of treatment. Disease assessments will consist initially of an MRI of the brain/pituitary and PET/CT (although a CT of the chest, abdomen and pelvis along with a bone scan is allowed if PET/CT is rejected by insurance). Clinical documentation of skin lesions with photography is highly encouraged. Measurement and documentation of all skin lesions is required even if photography is not performed. A repeat MRI is not required beyond baseline if the MRI at baseline is normal and there is no clinical suspicion of CNS or pituitary involvement. A bone marrow biopsy is only required if the patient has at least one cytopenia of grade 2 or greater at baseline or has evidence of bone marrow involvement on PET/CT. The bone marrow biopsy only needs to be repeated if abnormal at baseline.

Patients will be followed for 3 years (thirty-six months) from the initiation of therapy or until they initiate a new therapy for their underlying disease, whichever occurs first.

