10. STUDY CALENDAR

Baseline evaluations are to be conducted within 1 week prior to start of protocol therapy. Scans and x-rays must be done \leq 4 weeks prior to the start of therapy. In the event that the participant's condition is deteriorating, laboratory evaluations should be repeated within 48 hours prior to initiation of the next cycle of therapy.

Assessments must be performed prior to administration of any study agent. Study assessments and agents should be administered within \pm 3 days of the protocol-specified date, unless otherwise noted.

	Pre- Study	C1 D1	C1 D15	C2 D1	C2 D15	C3 D1	C3 D15	C4 D1	C5 D1	C6 D1	C7 D1	C8 D1	C9 D1	C10 & 11 D1	C12 D1	Off Treatment ^l	Follow Up ^m
Lenalidomide		Х	Х	Х	Х	Х	Х	Х	Х	Х	Х	Х	Х	Х	Х		
Anticoagulation		Х	Х	Х	Х	Х	Х	Х	Х	Х	Х	Х	Х	Х	Х	X ^h	
Informed consent	Х																
Demographics	Х																
Medical history	Х																
Concurrent meds			Х														X
Physical exam	Х	Х	Х	Х		Х		Х		Х		Х	Х		Х	Х	Х
Vital signs ^a	Х	Х	Х	Х		Х		Х		Х		Х	Х		Х	Х	Х
Height	Х	Х	Х	Х		Х		Х		Х		Х	Х		Х		Х
Weight	Х	Х	Х	Х		Х		Х		Х		Х	Х		Х	Х	Х
Performance status	Х	Х		Х		Х		Х		Х		Х	Х		Х	Х	Х
CBC w/diff, plts	Х	$\mathbf{X}^{\mathbf{j}}$	Х	\mathbf{X}^{j}	X^k	Х	X^k	Х		Х		Х	Х		Х	Х	Х
Serum chemistry ^b	Х	Х	Х	Х	X^k	Х	X^k	Х		Х		Х	Х		Х	Х	Х
EKG	Х																
Bone marrow biopsy	\mathbf{X}^{i}																\mathbf{X}^{i}
Adverse event evaluation			Х														X
Tumor measurements ^c	Х					Х				Х			Х		Х	Х	Х
Radiologic evaluation ^d	Х					Х				х			Х		Х	х	Х
B-HCG ^e	X ^b	Х		Х		Х		Х		Х		Х	Х		Х		Х
Urine/ Plasma Assay for BRAF mutation ^f	Xe					Х				х					Х	Х	Х
Serum TNF-alpha ^g	Х					Х				X					Х	Х	Х

a: Temperature, BP, HR and O2 saturation by pulse oximetry at rest.

b: Albumin, alkaline phosphatase, total bilirubin, bicarbonate, BUN, calcium, chloride, creatinine, glucose, potassium, total protein, SGOT [AST], SGPT [ALT], sodium.

c: Tumor measurements are repeated at C3D1, C6D1, C9D1 and C12D1 and then every 3 months thereafter until month 24. After month 24 tumor assessments will occur every 6 months (+/- 2 weeks) until month 36 from treatment initiation. Documentation (preferably radiologic) must be provided for participants removed from study for progressive disease. A window of +/- 1 week is allowed prior to month 24 but tumor assessments must occur prior to dosing on the relevant cycle when active treatment is being administered

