- CBC with automated differential will be checked every 7 days (+/- 1 day) during cycles 1 and 2; local labs are acceptable. Labs only necessary if dose escalation occurs. Note, these labs can be obtained at a local laboratory. Window for labs is +/- 3 days. k:
- Window for end of treatment visit is +/-7 days from the date of last dose. 1:
- The first follow up visit will occur 3 months from the date of last dose and then every 3 months thereafter. Window for follow up visits is m: +/- 2 weeks.

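### Four of the 11 cycle starts that depend on Day-1 blood counts have no count scheduled, and the aspirin dose and stopping time are stated in conflicting ways

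*Combined protocol and SAP*

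**What the plan says.** **Starting a cycle.** Section 5.2.2 opens with "A new course of treatment may begin on the scheduled Day 1 of a new cycle if" and then lists an ANC threshold, a platelet threshold and two conditions on resolution of drug-related toxicity. It continues: "If these conditions are not met on Day 1 of a new cycle, the subject will be evaluated weekly". The cycle is withheld until the problem resolves. Section 5.1 caps treatment at 12 cycles.

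**The calendar.** In Section 10 the row "CBC w/diff, plts" is blank at C5 D1, C7 D1 and the joint C10 & 11 D1 column. The lenalidomide row is marked in all three. Three other statements in Section 10 bear on blood counts:
- Footnote j: "CBC with automated differential will be checked every 7 days (+/- 1 day) during cycles 1 and 2; local labs are acceptable".
- Footnote k, attached to C2 D15 and C3 D15: "Labs only necessary if dose escalation occurs".
- The introduction: "laboratory evaluations should be repeated within 48 hours prior to initiation of the next cycle of therapy", but only for a participant whose condition is deteriorating.

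**Aspirin.** For patients not already on systemic anticoagulation, Section 1 says they are "required to take aspirin 325 mg daily for the duration of the protocol or for one month following treatment discontinuation, whichever is longer". Section 3.1.7 sets the eligibility test as "Able to take aspirin 81 mg daily as prophylactic anticoagulation". Section 5.4 requires 81 mg daily for as long as the study lasts. Calendar footnote h, in the off-treatment column, lets patients with no venous thromboembolic event and no other indication stop at that visit.

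**The concern.** The rule in Section 5.2.2 can be applied only if a current count is available. A team that follows the calendar reaches four cycle starts without one. It must then either notice the mismatch and order its own test, or start the cycle without the check that Section 5.2.2 demands.

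The supply route makes an unnoticed miss plausible. Sections 5.3 and 8.1.9 have the drug shipped to the patient one cycle at a time (Section 8.1.2 also allows shipment to the clinic), and Section 8.1.8 has it self-administered at home. A cytopenia without symptoms, which Section 5.2.2 would treat as a reason to delay, could therefore go unseen.

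The aspirin conflict concerns mandatory prophylaxis for a risk that Sections 1 and 5.4 both describe as known. Patients could receive different doses, or stop at different times, depending on which page is read.

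**Working it through.** **Part 1: blood counts**

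1. *Gated starts.* With at most 12 cycles (Section 5.1) and the rule applying after cycle 1 (Section 5.2.2), there are 12 − 1 = 11 gated starts, C2 to C12.

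2. *Calendar.* The header has 17 visit columns and the CBC row has 17 cells, so they align one to one. The Day-1 entries, with the joint C10 & 11 column split in two, are:

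| Day 1 of | C2 | C3 | C4 | C5 | C6 | C7 | C8 | C9 | C10 | C11 | C12 |
|---|---|---|---|---|---|---|---|---|---|---|---|
| Lenalidomide | X | X | X | X | X | X | X | X | X | X | X |
| CBC | X | X | X | – | X | – | X | X | – | – | X |

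3. *Count.* Seven starts have a scheduled CBC and four do not: 4/11 = 36.4%.

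4. *Ceiling for the trial.* If all 12 planned patients complete 12 cycles, there are 12 × 11 = 132 gated starts, of which 12 × 4 = 48 have no scheduled count.

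5. *Intervals.* At 28 days per cycle, the gaps between scheduled counts are:
   - C4 D1 to C6 D1: (6 − 4) × 28 = 56 days
   - C6 D1 to C8 D1: (8 − 6) × 28 = 56 days
   - C9 D1 to C12 D1: (12 − 9) × 28 = 84 days

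   The most recent scheduled count is therefore 28 days old at C5, C7 and C10, and 2 × 28 = 56 days old at C11. The calendar's ±3-day window cannot bridge that.

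6. *Does other text fill the gap?*
   - Footnote j stops after cycle 2.
   - Footnote k concerns only the C2 and C3 Day-15 laboratory tests.
   - The 48-hour repeat is limited to deteriorating participants.
   - The weekly CBC in the Section 6 dose-modification table (Table 3) begins only after a qualifying cytopenia has been found.
   - Footnote e provides for cycle starts without a clinic evaluation, but only for pregnancy tests.

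7. *Could the blanks be an artefact of text extraction?* This is unlikely. The cell count matches the header, and the serum chemistry and physical examination rows are blank at the same three columns.

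**Part 2: aspirin**

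| Place | Dose | Until |
|---|---|---|
| Section 1 | 325 mg, required | the longer of protocol duration and one month after treatment stops |
| Section 3.1.7 | 81 mg, ability to take it | not stated |
| Section 5.4 | 81 mg, required | study duration |
| Section 10, footnote h | none given | may stop at the off-treatment visit |

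Section 3.1.7 describes aspirin as prophylactic anticoagulation, so footnote h on stopping anticoagulation covers it. The doses differ by a factor of 325/81 = 4.0.

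The documents do not fix the size of the stopping-time gap. Footnote l places the off-treatment visit within 7 days either side of the last dose. Assume that one month is 30 days, that discontinuation is the date of the last dose, and that protocol duration ends with treatment. Footnote h then permits stopping earlier than Section 1 by:
- 30 − 7 = 23 days, with the visit 7 days after the last dose
- 30 days, with the visit on the day of the last dose
- 30 + 7 = 37 days, with the visit 7 days before the last dose

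If protocol duration includes follow-up (up to 3 years from treatment start, Section 5.6), the gap is longer.

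The text offers no tie-breaker. The venous thrombosis row of the Section 6 table points to a Section 5.6.1.2 on anticoagulation, but Section 5.6 covers duration of follow-up and has no such subsection.

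**The case against.** The strongest reply on blood counts is that this is a scheduling omission, not a missing safety rule. Section 5.2.2 still binds the investigator, unscheduled counts can be ordered, and footnote e suggests that the lighter visit schedule was deliberate. All of that is fair. It does not help a team working from the calendar, because footnote e supplies a substitute route for pregnancy tests and nothing equivalent exists for counts. The 48 of 132 is a ceiling, since progression and toxicity will end treatment early for some patients. The 4 of 11 per full course does not depend on that.

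On aspirin, Section 3.1.7 is worded as ability to take 81 mg, so the direct clash of requirements is Section 1 against Section 5.4. Sections 1 and 5.4 may largely agree on duration, because neither defines its term. Footnote h is permissive and restricted to certain patients. The 37-day figure needs an off-treatment visit before the last dose, which the literal window allows but is a strained reading; with a visit on or after the last dose the range is 23 to 30 days. These points narrow the conflict on stopping but do not remove it, and they leave the dose conflict untouched.

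Section 13.1 describes a single center, so differences would arise more between staff reading different pages than between centers. The two parts are unrelated to each other, and neither is claimed to affect the response endpoint. Each is nevertheless a contradiction in the current text.

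**Conclusion.** Both parts hold, and both must be fixed. Four of the 11 gated cycle starts (36%) have no scheduled blood count, up to 48 of 132 across the trial if all 12 patients complete 12 cycles. Intervals between scheduled counts reach 84 days on the nominal 28-day schedule. The two required aspirin doses differ fourfold, and footnote h permits stopping before the one-month minimum in Section 1. The 23-to-37-day size of that gap rests on the assumptions stated above and is illustrative only.

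This is more than missing detail. Following the calendar alone leaves Section 5.2.2 without its data, and the aspirin requirements in Sections 1 and 5.4 cannot both be met.

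**What to change.** Amend the protocol on two points.

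1. Reconcile Section 5.2.2 with the Section 10 calendar and its footnotes, so that the counts the rule depends on are scheduled whenever the rule applies. Footnotes j and k already accept local laboratories.
2. Reconcile Sections 1, 3.1.7 and 5.4 and calendar footnote h to one aspirin dose and one stopping time. Define whether protocol or study duration includes follow-up, and correct the reference to Section 5.6.1.2.

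Which statements stand is a clinical decision for the investigators; this review does not propose one. The cost is one amendment and, depending on how the count passages are reconciled, up to four extra blood draws per patient (at most 12 × 4 = 48 in total).
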